## 6.0 Clinical Evaluations

### 6.1 Schedule of Events

	Screen	Baseline*	Week 4	Week 12	Week 24*	Week 36	Week 48*	Early Discontinuation
Demographics	X							
Hormone therapy questionnaires		X						
Medical and medication history	X							
Targeted physical exam with weight, vital signs		X	X	X	X	X	X	
Complete physical exam and height	X							
DXA for bone mineral density, lean and fat mass		X					X	X
FibroScan for hepatic steatosis and fibrosis assessment		X					X	X
HIV-1 RNA	X		X	X	X		X	X
Safety labs**	X	X	X	X			X	X
CD4 + T lymphocyte count		X		X	X		X	X
Fasting lipids, banked serum and plasma samples for insulin and biomarkers		X			X		X	X
Medication dispensation		X	X	X	X	X		

\* Entry, week 24 and week 48 laboratory evaluations are required to be fasting (at least 8 hours)

\*\*Safety labs include: CBC with differential, chemistry panel including liver enzymes (ALT, AST, Alk Phos), total bilirubin and serum creatinine. All safety labs, HIV-1 RNA, and CD4+ T lymphocyte counts will be performed at local certified laboratories.

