### Premature Study Treatment/Background ART Discontinuation Evaluations

Participants who discontinue study drug due to an AE will be followed on-study off drug. The subject will complete all study evaluations and then be taken off study.

Participants who discontinue study drug for  $\geq 14$  days or who have confirmed virologic failure (two measurements  $> 200$  copies/mL) will complete the Discontinuation Visit evaluations and then be taken off study.

Similarly, participants randomized to Arm B who discontinue their entry ART regimen for  $\geq 14$  consecutive days will complete the Discontinuation Visit evaluations will and then be taken off study.

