### Targeted Physical Exam

A targeted physical examination at entry and all post-entry visits is to be driven by any previously-identified or new signs or symptoms that the participant has experienced since the last visit. This also includes weight, vital signs (temperature, pulse, respiration rate, and blood pressure), and diagnoses and medication updates at all visits.

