### **9.6.1 Primary Analysis**

Comparison between treatment arms of the primary endpoint will be undertaken using the Wilcoxon rank-sum test. The primary analysis will be as-treated, excluding participants who do not remain on the study regimen and/or participants who do not have an observed primary endpoint. Participants who discontinue study drug or their background entry regimen for  $\geq 14$  consecutive days will no longer contribute data to the primary outcome after the date on which they first discontinued medication. An intent-to-treat analysis will also be performed as a supplement.

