## **10.4 Serious Adverse Event Reporting**

The serious adverse event (SAE) reporting requirements and definitions for this study will be in keeping with local McGovern School of Medicine policies and in keeping with the sponsor's requirement. The study agent for SAE reporting is bictegravir + tenofovir alafenamide + emtricitabine. SAEs must be documented on the Serious Adverse Event Reporting form (SAE Reporting Form) available in the Manual of Procedure. [name] must be notified for any Grade 3 or greater toxicity that does not have a clearly documented etiology of not related to study drug. All Grade 4 events, death, persistent or significant disability/incapacity, hospitalization or prolongation of hospitalization, or event that the site investigator deems medically significant and thought to be related possibly, probably, or definitely related to study drug must be reported by completing and faxing the SAE Reporting form to [contact].

SAEs must be reported during the protocol-defined SAE Reporting period, which is from enrollment until four weeks following the subject's last dose of study drug. After the end of the protocol-defined SAE Reporting Period stated above, the site must report serious, unexpected, clinically-suspected adverse drug reactions if the site staff becomes aware of the event on a passive basis, i.e., from publicly available information.

All confirmed virologic failures will be reported immediately to the SMC. The SMC will also receive quarterly SAE reports for review.

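### Related Grade 3 or higher events first found at a Discontinuation Visit triggered by 14 days off regimen drop out of the as-treated tolerability endpoint, and the schedule and text disagree on the exam at that visit

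*Combined protocol and SAP*

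**What the plan says.** **Discontinuation rules.** Section 6.4 describes two routes. Participants who stop study drug because of an adverse event remain on study off drug and complete all evaluations. Those off study drug for 14 days or more, or with confirmed virologic failure, "will complete the Discontinuation Visit evaluations and then be taken off study". A parallel rule covers "participants randomized to Arm B who discontinue their entry ART regimen for" 14 or more consecutive days. Section 6.2 expects a Discontinuation Visit once 12 weeks of study drug have been completed.

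**Endpoint and analysis.** Section 9.3 builds the primary endpoint from HIV-1 RNA below 50 copies/mL, discontinuation for related adverse events, and related Grade 3 or higher laboratory or clinical events. Section 9.6.1 states: "The primary analysis will be as-treated, excluding participants who do not remain on the study regimen". It adds that those off regimen for 14 or more consecutive days "will no longer contribute data to the primary outcome after the date on which they first discontinued medication". It then says: "An intent-to-treat analysis will also be performed as a supplement". Section 9.6.2 reports treatment-related adverse events by arm through Week 48, with no cut-off at the stop date.

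**Schedule.** In the 6.1 table, safety labs are marked at screening, baseline, Weeks 4, 12 and 48, and Early Discontinuation. The row "Targeted physical exam with weight, vital signs" is marked at baseline and Weeks 4, 12, 24, 36 and 48, and is blank at Early Discontinuation. Section 6.5 says: "A targeted physical examination at entry and all post-entry visits is to be driven by any previously-identified or new signs or symptoms". Section 8.3 requires a closing safety evaluation for those who stop early after at least 12 weeks on drug.

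**SAE reporting.** Section 10.4 sets the reporting period as "from enrollment until four weeks following the subject's last dose of study drug".

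**The concern.** The day-14 rule in 6.4 sends the participant for laboratory work that measures components of the primary endpoint. The cut-off in 9.6.1 then discards those results, because it goes back to the first day off medication. For HIV-1 RNA that can be defended: a value drawn after the regimen was stopped does not describe the regimen. For tolerability it is harder to defend, because a related toxicity can surface, or first be measured, after the last dose.

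At stake is the tolerability half of the primary endpoint. The rule can only remove events from the as-treated count, never add them, so the regimen can only look as well tolerated as it is, or better. The blank exam cell matters in a different way. A site working from the table could omit the clinical assessment that the text requires, and that affects what is collected as well as what is counted.

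**Working it through.** The plan states no figure on this point, so there is none to reproduce. The check is date arithmetic plus a side-by-side reading.

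**1. Timing.** Let S be the first day off medication.
- Last day that counts under 9.6.1: S.
- First day the 14-day criterion of 6.4 is met: S + 14.
- A visit triggered by that criterion is on day V ≥ S + 14, so V − S ≥ 14 days.

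Examples: a stop on day 84 (Week 12) counts to day 84, with the visit on day 98 or later. A stop on day 252 (Week 36) counts to day 252, with the visit on day 266 or later.

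**2. The two sentences of 9.6.1.** One excludes participants who leave the regimen; the other lets them contribute up to the stop date. The text does not say which governs. Under either one, results from day V do not enter the as-treated analysis.

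**3. Which events are lost.**
- The event that prompts the stop occurs on or before S. Under the second sentence it is kept.
- A clinical event with onset before S but reported at the visit might be kept. Section 9.6.1 does not say whether the cut-off uses onset date or detection date.
- A laboratory abnormality first seen at the visit carries the draw date, which is after S. It is lost. So is any related event with onset after S.

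**4. What else could have caught it.** After Week 12 the next scheduled safety panel is Week 48. For a stop at Week 40, the last countable scheduled panel is 40 − 12 = 28 weeks earlier. For a stop just before Week 48 the gap approaches 48 − 12 = 36 weeks. The Early Discontinuation panel is the only scheduled one that could fill this gap. (Lipids and glucose are also measured at Week 24, and targeted exams take place at Weeks 24 and 36. The gap concerns the blood count, liver enzymes, bilirubin and creatinine.)

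**5. Size.** Inputs from 9.1: 24 enrolled per arm, 20 evaluable, up to 20% loss.
- Upper bound on participants affected: 0.20 × 24 = 4.8 per arm (0.20 × 48 = 9.6 in total).
- One uncounted event: 1/24 = 4.2 percentage points, or 1/20 = 5.0 points with 20 evaluable.

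The bound is generous. It includes participants lost to follow-up, who have no visit, and those who stop before 12 weeks. The share who would meet the 14-day criterion and have a related event first found at the visit is not given.

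**6. Exam at Early Discontinuation.**

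| Source | Exam at this visit |
|---|---|
| 6.1 table | not marked |
| 6.5 | required at every visit after entry |
| 8.3 | closing safety evaluation after at least 12 weeks on drug |

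The table and the text conflict. The conflict bears on clinical events only, since HIV-1 RNA and safety labs are both marked in that column.

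**The case against.** Ending as-treated data at the stop date and adding an intent-to-treat supplement is a recognised choice, and this is a small pilot whose analyses are declared exploratory. That stands for HIV-1 RNA. It does not justify dropping related toxicity from a tolerability endpoint.

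Several stronger readings are tempting, and the documents do not support them:
- *The visit cannot inform the primary endpoint at all.* Only the as-treated analysis is closed to it. The intent-to-treat supplement and the 9.6.2 summary carry no stop-date cut-off.
- *The visit always comes two weeks or more after the stop, and off all ART.* No visit date is set, so a participant who announces a stop may be seen sooner. The trigger is stopping study drug or the entry regimen, and another regimen may have been started. Confirmed virologic failure is a separate trigger that can occur on drug.
- *The toxicity that causes a stop is lost.* It falls on or before the cut-off, and 6.4 keeps adverse-event stoppers on study. Even so, the 9.6.1 cut-off makes no exception for them once they are off drug for 14 days, so later findings in them are also uncounted.
- *Signs and symptoms would not be recorded at the visit.* Section 6.5 requires Grade 2 or higher signs and symptoms after entry whatever the table shows.
- *Section 10.4 contradicts 9.6.1.* Section 10.4 defines an SAE reporting period, not an analysis window.

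The long interval between safety panels arises from the schedule itself, not from the cut-off. It is cited here only because it makes the Early Discontinuation panel more valuable.

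**Conclusion.** The point holds within limits. When 14 days off regimen triggers the Discontinuation Visit, a related Grade 3 or higher event first detected there is left out of the as-treated tolerability endpoint. The effect on the count is downward or nil. Which arm it favours cannot be told from the documents. At the plan's own loss assumption at most about 4.8 of 24 per arm could be affected, and probably fewer. This rests on the 14-day criterion being the trigger and on laboratory findings being dated by the draw.

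The blank exam cell in 6.1 is a genuine conflict with 6.5 and 8.3, but it does not touch the laboratory components. Section 6.4 also leaves open whether an adverse-event stopper who is off drug for 14 days or more stays on study or leaves it. Both conflicts need reconciling. The changes are worth making because they cost little and affect a primary endpoint.

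**What to change.** 1. **Section 9.6.1.** Apply the stop-date cut-off to HIV-1 RNA only. Count tolerability events detected up to and including the Discontinuation Visit, or within a stated window after the last dose, in both arms. The four weeks already used for SAE reporting in 10.4 would serve; in Arm B they should run from the last dose of the entry regimen. Word the exclusion sentence so that it does not remove these participants from the tolerability component.
2. **Section 6.4 and the CRF.** Record the last-dose date and whether the participant was on any ART at the draw. Take the draw as near the last dose as practicable. Flag HIV-1 RNA and biomarker samples taken off ART.
3. **Section 6.1.** Reconcile the Early Discontinuation column with 6.5 and 8.3 on the targeted exam.
4. **Section 6.4.** Reconcile the paragraph keeping adverse-event stoppers on study with the one taking participants off study at 14 days.

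Cost: a few sentences in 6.4 and 9.6.1, one table cell, and CRF fields for the last-dose date and ART status. No visit is added. Reported tolerability may be slightly less favourable, and participants who stop without telling the site will still be seen late.

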## 6.5 Clinical Assessments

### Documentation of HIV

HIV-1 infection, as documented by any licensed ELISA test kit and confirmed by Western blot at any time prior to study entry. HIV-1 culture, HIV-1 antigen, plasma HIV-1 RNA, or a second antibody test by a method other than ELISA are acceptable alternative confirmatory tests. This does not need to be recorded on a CRF.

### Medical History

The medical history must include all AIDS-related diagnoses, any active diagnoses, and history of any major illnesses (eg, coronary artery disease, hypertension, diabetes, stroke, malignancy, auto-immune disorders). Any allergies to any medications and their formulations must be documented. Surgeries that are planned prior to the time of the subject's informed consent will also be documented. Current and previous smoking history and alcohol and drug use history will also be collected.

### Medication History

A medication history must be recorded in the source documents and the CRF. The medication history will include the following:

- Complete HIV treatment history, including start and stop dates of any current or past ART regimens (estimated if the exact dates cannot be obtained), immune-based therapy, or HIV-related vaccines, including blinded study medications. For patients who are not on their first ART regimen, documentation must be provided that ART medications were not switched secondary to virologic failure (verbal confirmation okay if documented on the CRF). Any available genotypic or phenotypic information should also be included.
- All prescription medications (in addition to those noted above) taken in the 30 days prior to study entry, including actual or estimated start and stop dates.
- Nonprescription medications taken in the 30 days prior to study entry. Include actual or estimated start and stop dates.
- Alternative therapies and dietary supplements taken in the 30 days prior to study entry. Include actual or estimated start and stop dates.

### Complete Physical Exam

A complete physical examination is required at screening and includes: examination of the skin, head, mouth, and neck; auscultation of the chest; cardiac exam; abdominal exam; examination of the lower extremities for edema. The exam also includes documentation of signs and symptoms, diagnoses, vital signs (temperature, pulse, respiration rate, and blood pressure), height and weight.

### Targeted Physical Exam

A targeted physical examination at entry and all post-entry visits is to be driven by any previously-identified or new signs or symptoms that the participant has experienced since the last visit. This also includes weight, vital signs (temperature, pulse, respiration rate, and blood pressure), and diagnoses and medication updates at all visits.

### Height

Height in stocking feet will be recorded on the CRF at the screening visit only. If not obtained at screening for any reason, height must be documented at the entry visit.

### Signs and Symptoms

At entry, record all signs and symptoms occurring in the 30 days prior to entry. After entry, record all signs and symptoms  $\geq$  Grade 2. This study will use the most current DAIDS toxicity grading system. Any signs or symptoms that lead to a change in the study drug, regardless of grade, must also be recorded.

### Diagnoses

Record all diagnoses identified in Complete Physical Exam, above. Diagnosis recording should be standardized by using the ACTG Criteria for Clinical Events and Other Diseases. All confirmed and probable diagnoses made since the last visit will be recorded.

### Concomitant Medications

All concomitant medications taken since the last visit will be recorded in the source documents. Only prescription medications will be recorded on the CRFs.

### Antiretroviral Medications

All modifications to antiretroviral medications including initial doses, subject-initiated and/or protocol-mandated interruptions, modifications, and permanent discontinuation will be recorded on the CRFs.

### Study Treatment Modifications

Modifications of all ART including study treatment, initial dose, subject-initiated, and/or protocol-mandated modifications as well as permanent discontinuation will be recorded on the CRFs. If a subject misses more than 4 consecutive doses, the study treatment is considered modified and this must be reported appropriately on the CRF.

### DXA

Whole body DXA will be performed and read locally using standardized procedures. Total lean, appendicular lean, total fat, trunk fat and appendicular fat measurements will be recorded in addition to bone mineral density. These scans are not being performed for clinical care, but TW will be offered a copy of the report to provide to their physician.

### FibroScan

FibroScan will be performed and interpreted by [name], with CAP and LSM measurements recorded. As per standard protocol, 10 measurements with a LSM interquartile range (IQR) <30% per TW will be obtained. Scans will occur in the TSHC procedure room. All TW will have LSM and CAP assessments. These scans are not being performed for clinical care, but TW will be offered a copy of the report to provide to their physician.

### Questionnaires

Questionnaires will be administered for 1) self-report of basic demographic information and 2) female hormone therapy type, frequency and mode of acquisition.

## **6.6. Laboratory Evaluations**

Fasting will be required for study entry and weeks 24 and 48. Fasting will be defined as nothing by mouth except water and medications for at least 8 hours prior to the lab draw. At screening and entry, all laboratory values, regardless of grade, must be recorded on the CRFs. For post-entry assessments, record all laboratory values for WBC, Hb, platelet, glucose, creatinine, AST, ALT, lipid profile, CD4+ T lymphocyte count and HIV-1 RNA, and any other  $\geq$  Grade 2 laboratory value. Any laboratory value leading to a change in ART treatment must be recorded regardless of grade. Fasting lab studies include: total cholesterol, LDL cholesterol, triglycerides, HDL cholesterol, glucose (at weeks 0, 24 or 48), insulin and all biomarker measurements.

The site must refer to the Division of AIDS Table for Grading the Severity of Adult and Pediatric Adverse Events (DAIDS AE Grading Table), Version 2.0, November 2014, which is available on site.

### Fasting lipids, glucose, insulin

Fasting total cholesterol, HDL cholesterol, LDL cholesterol (direct), triglycerides and glucose will be performed at entry and weeks 24 and 48 in real time at the local laboratory. Samples for insulin and oxidized LDL measurement will be batched and analyzed at the end of the study.

### Plasma HIV-1 RNA

HIV-1 RNA must be performed by a laboratory that possesses a CLIA certification or equivalent. Eligibility will be determined based on the screening value.

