## **4.0 Selection and enrollment of participants**

### **4.1 Inclusion Criteria**

- 4.1.1 Self-identified TW
- 4.1.2 Age 18 or older
- 4.1.3 Confirmed HIV-1 infection
- 4.1.4 HIV-1 RNA <50 copies/mL at screening and for ≥24 weeks prior to entry. Participants with a single “blips” to HIV-1 RNA <500 copies/mL will be permitted to enroll.
- 4.1.5 Current ART with 2 NRTIs (TDF, TAF or ABC with FTC or 3TC) *and a 3rd agent*. Study participants are not required to be on their first regimen. However, patients who are not on their first ART regimen must not have previously substituted drugs secondary to known resistance to integrase inhibitors or components of their NRTI backbones. Other reasons for substitution such as medication intolerance or patient preference are acceptable. No changes in ART in the 12 weeks prior to screening.
- 4.1.6 Current female hormone therapy use.
- 4.1.7 Ability and willingness of subject to provide informed consent.

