### Visit 2 Baseline (within 45 days of screening)

Once eligibility has been confirmed, the subject will be randomized 1: 1 to either:

ARM A: Immediate switch of current ART to bictegravir + tenofovir alafenamide + emtricitabine for 48 weeks.  
or

ARM B: Continue current ART unchanged for 48 weeks.

Visit windows for all subsequent visits will be +/- 14 days from the expected date.

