### Fasting Stored Serum and Plasma

If participants come to the appointment and are not fasting, they will need to come back in fasting state for these evaluations within a 7-day window.

Serum (three 1 mL aliquots) and plasma (three 1 mL aliquots) will be collected as indicated in the schedule of events (entry, week 24, week48). Additionally, please collect 3mL of both serum and plasma in the event of study discontinuation and/or virologic failure. Frozen specimens will be collected, labeled with patients' PID, study week # and date of draw, and stored in a -70 degrees Celsius until batched processing can occur. The stored samples will be used for future measurements of metabolic and inflammatory markers which may include but are not limited to adiponectin, IL-6, IL-1B, PAI-1, and d dimer.

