## 9.3 Primary Endpoint Assessments

The safety (frequency of maintaining HIV-1 RNA <50 copies/mL) and tolerability (frequency of study drug discontinuation due to study-drug related AEs and frequency of study-drug related ≥ Grade 3 lab or clinical events whether or not study drug was discontinued) of bictegravir + tenofovir alafenamide + emtricitabine in HIV-infected TW on female hormone therapy vs continued ART.

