## **9.6 Analyses**

A descriptive analysis of demographic and clinical characteristics will be generated. Continuous variables will be expressed as mean  $\pm$  SD if normally distributed or median with IQR if not normally distributed. Data will be pooled by arm and stratified by ART 3rd drug class. CAP will be used continuously and categorically, using for the latter the following standardized steatosis cut-offs: Grade 1 238 dB/m, Grade 2 260 dB/m and Grade 3 292 dB/m. DXA data will be used continuously for lean and fat mass measurements, and, for bone mineral density, both continuously and categorically, with the latter using standard cutoffs for osteopenia and osteoporosis. Biomarker levels may be log-transformed, where appropriate. Wilcoxon rank-sum and Pearson  $\chi^2$  tests will compare continuous and categorical variables, respectively, between and within groups. Although the sample size is small, regression modeling will be attempted to assess if any observed differences persist after adjustment for confounding factors. All statistical tests will be 2-sided ( $\alpha=0.05$ ). Analysis will be exploratory without adjusting for multiple testing. [name] and [name] (statistician) will oversee analysis plan development/implementation.

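### No HIV-1 RNA is measured at randomisation, and no value is named as the baseline for the primary-endpoint component on maintained suppression

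*Combined protocol and SAP*

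**What the plan says.** - **Eligibility on RNA.** Inclusion criterion 4.1.4 requires "HIV-1 RNA <50 copies/mL at screening and for ≥24 weeks prior to entry". Its next sentence makes an exception for a single blip: such people, with a rise "to HIV-1 RNA <500 copies/mL will be permitted to enroll". The timing of the blip is not given. Section 6.6 (Plasma HIV-1 RNA) adds "Eligibility will be determined based on the screening value".
- **Screening to entry.** Section 6.2 has "Visit 2 Baseline (within 45 days of screening" and a window of 14 days either side for later visits.
- **RNA schedule.** The table in Section 6.1 marks RNA at screening, Weeks 4, 12, 24 and 48, and early discontinuation. The Baseline cell is empty. The same column has CD4 count, safety labs, fasting lipids and banked serum and plasma.
- **Endpoint.** Section 9.3 opens with "The safety (frequency of maintaining HIV-1 RNA <50 copies/mL". Neither it nor Section 9.6 says which RNA value is the baseline, or at which visit or visits maintenance is judged.
- **ART stability.** Criterion 4.1.5 ends with "No changes in ART in the 12 weeks prior to screening". The windows in 4.1.4 and 4.2.2 run to entry.

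**The concern.** Maintaining suppression presupposes a known starting state. Here the starting state at randomisation is inferred from an earlier sample. If someone's RNA rises between screening and Baseline, the first scheduled value that can show it is Week 4, after Arm A has switched regimen. That value cannot say whether viraemia began before or after the switch. In an open-label switch study the natural reading is that the new regimen failed. If two values above 200 copies/mL follow, the event is a confirmed virologic failure, which Section 10.4 sends immediately to the monitoring committee. Under Section 6.4 the person then leaves the study. Depending on how Section 9.6.1 is applied, they either count against the arm or drop out of the as-treated set. With at most 24 people per arm, one such case is visible in the result.

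The protocol gives reason to take the interval seriously: Section 9.1 calls the population high-risk, and Section 2.1 describes unstable housing and daily schedules as frequent.

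**Working it through.** **1. The plan's own figure.** The only power statement with all inputs given is for CAP (Section 9.1): difference 56 dB/m, SD 53, 20 per arm, alpha 0.05 (Section 9.6: "All statistical tests will be 2-sided"). Standardised difference = 56/53 = 1.057. Normal approximation: power = Φ(1.057 × √(20/2) − 1.96) = Φ(1.38) = 91.6%. A two-sample t-test gives 90.2%. The stated 90% reproduces. It concerns a secondary endpoint and does not depend on this point. No power, margin or expected rate is given for RNA below 50.

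**2. Longest interval without an RNA result.**
- Screening to Baseline: up to 45 days (Section 6.2).
- Baseline to the latest permitted Week 4 visit: 28 + 14 = 42 days.
- Total: 45 + 42 = 87 days.

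With an RNA at Baseline, the value is current on the day of entry, and the longest wait to the next one is 42 days.

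**3. Weight of one person.** 1/24 = 4.2 percentage points of an arm as enrolled; 1/20 = 5.0 points of an arm after the planned losses. Both apply only if the person is counted as a failure.

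**4. Chance imbalance.** Suppose 2 of 48 are unsuppressed at entry and arms are exactly 24 each. The chance that both fall in the same arm is 23/47 = 49%. If both count as failures, that alone separates the arms by 2/24 = 8.3 points. For 3 people, the chance that all fall in one arm is (23 × 22)/(47 × 46) = 23%.

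**5. How often it might happen.** The documents give no figure for the share p with RNA of 50 or more on the day of entry. The values of p below are assumptions, shown only to give a range.

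| Assumed p | Expected among 48 (48p) | At least one in Arm A, 1 − (1 − p)^24 | At least one in the trial, 1 − (1 − p)^48 |
|---|---|---|---|
| 1% | 0.5 | 21% | 38% |
| 2% | 1.0 | 38% | 62% |
| 5% | 2.4 | 71% | 91% |
| 10% | 4.8 | 92% | 99% |

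These are chances that such a person is present. They do not measure an effect on the comparison.

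**The case against.** The strongest reply is that the trial does have pre-randomisation RNA data. Everyone has a screening value, 4.1.4 adds a suppression history of at least 24 weeks, and Section 6.2 allows medical records to be requested to confirm eligibility. A reader might infer that the endpoint has no baseline at all. The documents do not support that: what is missing is a value at randomisation and a statement of which value serves as baseline.

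Other stronger readings also go too far:

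- **Biased comparison.** Anyone unsuppressed at entry became so before allocation, so the arms are balanced in expectation. Only chance imbalance and interpretation remain, in a pilot whose analysis is described as exploratory.
- **A Week 4 rebound is automatically a failure.** Section 9.3 does not fix the visit at which maintenance is judged. Someone above 50 at Week 4 and below 50 at Week 48 might not count as a failure. Confirmed failure needs two values above 200, so a low transient value triggers neither the committee report nor withdrawal.
- **The blip clause admits a viraemic screen.** This reading sets the second sentence of 4.1.4 against the first, which requires a value below 50 at screening, and against Section 6.6, which makes that value decisive. The wording leaves it possible; the more natural reading is that the exception qualifies the 24-week history.
- **ART may change between screening and entry.** The text is silent, which is not permission. Arm B is to continue its current ART unchanged, and Section 6.5 has medication updates at entry and ART modifications recorded on the CRF, so a change should be visible.
- **No sample could ever settle the question.** Plasma is banked at Baseline and frozen. But its stated use is metabolic and inflammatory markers, and no RNA test on it is planned.

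A further fair objection is that a Baseline assay that does not hold up randomisation will not keep an unsuppressed person out. That stands. The assay helps interpretation; it is not an extra eligibility gate.

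**Conclusion.** The point holds as a gap in measurement and definition. RNA is not scheduled at randomisation, the qualifying value may be 45 days old, up to 87 days may pass before the first on-study value, and none is designated as baseline for a primary-endpoint component that depends on a starting state. As planned, viraemia present at entry cannot be separated from failure after the switch.

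The size is 4.2 to 5 points of an arm's rate per affected person, conditional on that person being counted as a failure. The number of such people is unknown. The expected between-arm difference is not biased, and CAP power is unaffected. The schedule facts are certain; the practical effect depends on an unstated entry rate and an undefined endpoint visit. This is a cheap improvement worth making, not a flaw that undermines the design. The blip and ART-stability wordings are secondary points for clarification.

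**What to change.** 1. Add HIV-1 RNA to the Baseline column of Section 6.1, taken with the blood already drawn at that visit and before the first dose of study drug. Randomisation need not wait for the result.
2. In Section 9.3, name the Baseline RNA as the baseline value for the suppression component.
3. In Section 9.6.1, keep the analysis of all participants and prespecify a supplementary analysis of maintained suppression restricted to those with Baseline RNA below 50 copies/mL.
4. As clarifications, reconcile the blip sentence in 4.1.4 with the screening requirement before it and with Section 6.6. Reconcile the end of the ART-stability window in 4.1.5 (screening) with the entry anchor in 4.1.4 and 4.2.2. Which eligibility rule is intended is for the sponsor and investigator to state.

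**Cost.** About 48 RNA assays (plus any for replaced participants), no extra visit and no delay to randomisation. The supplementary set will be slightly smaller than the full set, which is why it should supplement the analysis of everyone and not replace it.
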